
Exclusion Criteria
	
 1. Previous H. pylori eradication therapy 2. Less than 18 years old 3. With history of H. pylori infection treatment 4. With previous gastric surgery 5. Major systemic diseases 6. Pregnancy or lactation 7. Allergy to any of the study drugs 8. Administration of antibiotics, bismuth, antisecretory drugs in 8 weeks prior to inclusion

Arms and Interventions
	
1. Empirical therapy
 
Esomeprazole 20 mg, bismuth potassium citrate 600 mg taken twice a day, amoxicillin 1 g, and metronidazole 500 mg taken three times a day for 14 days.
 
2. Tailored therapy
 
Tailored therapy is based on antimicrobial susceptibility of clarithromycin, metronidazole and levofloxacin. according to antibiotic resistance pattern included esomeprazole 20mg bid, amoxicillin 1g bid, with a third drug (clarithromycin 500mg bid, metronidazole 400mg bid, or levofloxacin 500mg qd) for susceptible strains, or with bismuth 220mg bid plus metronidazole 400mg qid for triple-resistant strains. Study treatment regimens were all given 14 days.

Schedule
	
1. Enrollment
 
Obtain written informed form

	
Check eligibility criteria
 
Collect baseline characteristics
 
Undergo upper endoscopy with gastric biopsy and rapid urease testing
 
Conduct bacterial culture and antibiotic susceptibility testing
 
2. Allocation
 
After the written informed consents would be obtained from eligible patients, the independent research assistant will open envelopes by randomization sequence and telephone study staff to give them each patient's treatment allocation. Eligible patients will be randomly allocated to receive either tailored therapy or empirical therapy in a 3:1 ratio.
 
3. treatment
 
Study treatment regimens were all given 14 days. During the treatment period, the subjects kept a diary to monitor compliance and symptoms.
 
4. Follow-up
 
After the end of treatment, adverse events and compliance was surveyed. Six weeks after completion of therapy, H. pylori eradication was assessed by ¹³C-urea breath testing.

Outcome Measures
	
Primary Outcome Measure:
 
1. Helicobacter pylori eradication rate
 
Six weeks after completion of therapy, H. pylori eradication success is defined as negative result from urea breath test (<4%)
 
Secondary Outcome Measure

Final Protocol

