6.2 Intervention

(1) Empirical therapy

Esomeprazole 20 mg, bismuth potassium citrate 600 mg taken twice a day, amoxicillin 1 g, and metronidazole 500 mg taken three times a day for 14 days.

(2) Tailored therapy

Tailored therapy is based on antimicrobial susceptibility of clarithromycin, metronidazole and levofloxacin. a) If the H. pylori strain of one patient was sensitive to clarithromycin, clarithromycin triple therapy (EAC) will be given: esomeprazole 20 mg, amoxicillin 1 g, and clarithromycin 500 mg taken twice a day; b) If the strain was resistant to clarithromycin but sensitive to metronidazole, metronidazole triple therapy (EAM) will be given: esomeprazole 20 mg, amoxicillin 1 g, and metronidazole 500 mg taken twice a day. c) If the strain was resistant to both clarithromycin and metronidazole but sensitive to levofloxacin, levofloxacin triple therapy (EAL) will be given: esomeprazole 20 mg, amoxicillin 1 g taken twice a day, and levofloxacin 500 mg taken once a day. d) If the strain was resistant to all three antibiotics, bismuth quadruple therapy (EBA₂M₄) will be given: esomeprazole 20 mg, bismuth potassium citrate 600 mg, amoxicillin 1 g taken twice a day, and metronidazole 500 mg taken four times a day. Study treatment regimens will be all given 14 days.

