8.2 Records and follow-up of AE

During the study, AE will be accurately recorded, including the time of occurrence, severity, duration, the measures taken and the outcome. Researchers will follow all the AE until the symptoms of patients disappeared or condition become stable. SAE should be tracked until a proper solution is found even though the study is over.

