5.1 Rate of adverse events

During the 14-day treatment period, the subjects will keep a diary to score any possible side effects or discomforts. The subjects will be asked to grade the severity of adverse events according to their influence on daily activities, experienced as "mild" (transient

and well tolerated), “moderate” (causing discomfort and partially interfering with daily activities), or “severe” (causing considerable interference with daily activities). The side effect score recorded is based on the most severe event. Rate of adverse events is defined as the number of patients with any adverse event divided by the total number of population for analysis. These data are presented with number, percentage.

Comparisons of presence of each adverse event and any adverse event between the tailored therapy and empiric therapy will be performed in the safety analysis populations using the Pearson’s χ^2 , corrected χ^2 or Fisher’s exact test.

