5.2 Compliance rate

Compliance was defined as either poor when they had taken less than 80% of the total medication or good when they had taken more than 80% medication. Compliance rate is defined as the number of patients with good compliance divided by the total number of population for analysis. These data are presented with number, percentage.

Comparisons of presence of each adverse event and any adverse event between the tailored therapy and empiric therapy will be performed in the ITT analysis populations using the Pearson’s χ^2 , corrected χ^2 or Fisher’s exact test.

5.3 Other Pre-specified Outcome Measures:

(1) Medical cost per patient of tailored or empiric therapy

Medical cost of one patient is overall cost including visit, endoscopy, H. pylori culture, susceptibility testing, eradication treatment, and adverse event treatment.

Comparisons of medical cost between the tailored therapy and empiric therapy will be performed in the PP analysis populations using Student t test.

(2) Ratio of medical cost to H. pylori eradication rate of each therapy

Ratio of medical cost to H. pylori eradication rate of each therapy is defined as average medical cost of the therapy divided by H. pylori eradication rate of one therapy.

(3) Ratio of incremental medical cost to incremental H. pylori eradication rate of tailored compared with empiric therapy

If one therapy cost less and achieved higher eradication rate than the other one, it will be referred to as dominant strategy. If one therapy yielded higher eradication rate but also cost more, an incremental cost-effectiveness ratio (ICER) will be calculated. Obviously, the tailored therapy will cost more because of additional bacterial culture and antibiotic susceptibility testing. So, if eradication rate of the tailored therapy was higher, the ICER of the tailored therapy will be calculated as the ratio of incremental medical cost to incremental H. pylori eradication rate of tailored compared with empiric therapy (in terms of RMB per incremental eradication percentage). If eradication rate of the tailored therapy was equal to or lower than the empiric therapy, the tailored therapy will not be more cost-effective option and the economic evaluation will not be conducted.

6. Additional analyses

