6.2 Effect of antibiotic resistance on eradication rate

Comparisons of eradication rate of one therapy between antibiotic susceptible and

resistant strains will be performed in the PP analysis populations using the Pearson's χ^2 , corrected χ^2 or Fisher's exact test.

Additional comparisons of eradication rate of antibiotic resistant strains between the tailored therapy and the empiric therapy will be performed in the PP analysis populations using the Pearson's χ^2 , corrected χ^2 or Fisher's exact test.

6.3 Effect of presence of adverse events on compliance.

Comparisons of compliance rate of one therapy between presence and absence of adverse event will be performed in the safety analysis populations using the Pearson's χ^2 , corrected χ^2 or Fisher's exact test.

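### Final SAP 6.3 tests the effect of adverse events on compliance without requiring the event to come first, so it understates a harmful effect

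*Combined protocol and SAP*

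**What the plan says.** The Final SAP lists this among its additional analyses, under the heading "6.3 Effect of presence of adverse events on compliance". The method is one sentence: "Comparisons of compliance rate of one therapy between presence and absence of adverse event will be performed in the safety analysis populations", by chi-square or Fisher's exact test. Table 5 carries it, with good adherence split by AE status under a p-value column.

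The outcome comes from Final SAP 5.2: "Compliance was defined as either poor when they had taken less than 80% of the total medication". The course is fixed in Final Protocol 6.2: "Study treatment regimens will be all given 14 days". Final SAP 5.1 takes AEs from the same period: "During the 14-day treatment period, the subjects will keep a diary to score any possible side effects or discomforts". It counts patients with any event: "Rate of adverse events is defined as the number of patients with any adverse event divided by the total number of population for analysis". Final Protocol section 8 defines AEs more widely, from consent to one month after treatment. Final SAP 6.3 does not say which window decides who counts as having had an AE.

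Some timing information is collected. Final Protocol 8.2 says "AE will be accurately recorded, including the time of occurrence, severity, duration" and more will be recorded. The Schedule in the Final Protocol abstract says "During the treatment period, the subjects kept a diary to monitor compliance and symptoms". Neither enters the test. Table 5 also has a separate row counting, by arm, patients who discontinued drugs because of AEs.

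**The concern.** Exposure and outcome build up over the same 14 days. A patient who stops on day 4 for an unrelated reason has 4 days on drug in which a drug-related AE can appear; a complier has 14. The outcome thus influences the exposure group: stopping early makes it more likely that a patient is classed as having no AE. An AE that begins after the stop, if counted, is treated as though it could have caused the stop. Running the test within one therapy does not help, because the problem arises even when every patient has the same regimen.

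At stake is the answer on how two secondary outcomes, AE rate and compliance rate, relate to each other. A heading that says effect, with a p value beside the split, invites a causal reading. The result may then suggest that AEs matter less for adherence than they do.

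**Working it through.** Final SAP 6.3 states no figure, so there is none to reproduce.

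**Inputs from the documents.** Course of 14 days, threshold 80%, recruitment of 286 and 96. Since 0.80 × 14 = 11.2 days, a full stop after day 11 gives 11/14 = 78.6% (poor) and after day 12 gives 12/14 = 85.7% (good).

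**Assumptions (not in the documents).** 40% of full-course patients have an AE. The daily AE hazard is then h = −ln(1 − 0.40)/14 = 0.0365.

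**Step 1: no true effect.** Let 5% comply poorly, with stop days spread evenly over days 1 to 11 and unrelated to AEs. If AEs arise only on drug, the chance of an AE in a poor complier is the mean of 1 − exp(−h·d) over d = 1 to 11, which is 0.191. Then:

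- Poor compliance given an AE: 0.05 × 0.191 / (0.05 × 0.191 + 0.95 × 0.40) = 2.5%
- Poor compliance given no AE: 0.05 × 0.809 / (0.05 × 0.809 + 0.95 × 0.60) = 6.6%
- Ratio: 0.37, where the truth is 1

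**Step 2: true effects.** Follow patients day by day. Each day an AE-free patient on drug has an AE with probability 1 − exp(−h). On days 1 to 11 a patient stops with probability 0.0035 if AE-free and 0.0035·k after an AE. The planned ratio is the proportion of poor compliers among patients with an AE divided by the proportion among those without.

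| Setting | True k = 1 | k = 2 | k = 3 |
|---|---|---|---|
| AEs only on drug, constant hazard | 0.37 | 0.73 | 1.06 |
| AEs after stopping at half the on-drug rate | 0.66 | 1.08 | 1.46 |
| Half of poor compliers miss scattered doses and stay on drug | 0.64 | 1.06 | 1.43 |
| 70% of the AE hazard in days 1 to 3 | 0.67 | 1.34 | 1.95 |
| AEs after stopping at the full on-drug rate | 1.00 | 1.46 | 1.92 |
| Person-day stopping rate after v before first AE | 1.0 | 2.0 | 3.0 |

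The second decimal moves by about 0.02 with the day convention. A continuous clock closing at day 11 lowers the first five entries for k = 2 to about 0.65, 1.02, 0.98, 1.22 and 1.43.

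**Step 3: wider ranges.** With constant hazards and AEs only on drug, AE risks of 20% to 50% and AE-free stopping of 3% to 10% give 0.67 to 0.81 for a true doubling and 0.99 to 1.18 for a tripling. If stops fall only in days 1 to 4 (AE-free stopping 3% to 5%), even a five-fold effect reads 0.66 to 0.81. If instead 90% of the AE hazard falls in days 1 to 4, a doubling reads 1.43 to 1.54.

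**Step 4: events available.** At 5% poor compliance, 0.05 × 96 = 4.8 patients in the empiric arm and 0.05 × 286 = 14.3 in the tailored arm.

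**The case against.** The strongest reply is that size and direction depend on things the documents do not give. A reader might infer that a three-fold effect will read as none, or that the analysis will show AEs improving adherence. That needs a roughly constant AE hazard, poor compliance that is always a full stop, and no AEs after stopping. The text supports none of these. Poor compliance is a share of total medication in multi-drug regimens, so scattered missed doses qualify. Neither the 14-day diary nor the one-month AE window is shortened when a patient stops; only time on drug is. This stands: reversal is conditional.

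Second, the Table 5 row on discontinuation because of AEs addresses the question more directly. That partly stands. The row counts attributed stops by arm, but it misses shortfalls that are not full stops, and it neither enters nor corrects the 6.3 test.

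Third, a time-varying Cox model would be out of proportion. That stands. About 5 stops are expected in the empiric arm. In simulation under no effect, one exposure group had no stop in about 37% of trials with 96 patients.

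Fourth, 6.3 is an additional analysis and not a listed outcome. That limits the consequence but does not make the estimate right. Under the least favourable no-effect model, Fisher's test rejects falsely in about 22% of arms of 286 (about 2% at 96).

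**Conclusion.** The point holds as a bias towards understating harm. Followed exactly, Final SAP 6.3 ignores the order of AE and shortfall, and no other section supplies a rule. Under the assumed 40% AE risk and 0.0035 daily stopping hazard, every setting examined pulls a true doubling below 2, from about 0.73 to 1.46. Only some of them bring it to about 1 or below. Scattered missed doses in place of full stops reduce the bias.

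The documents do not support saying that the effect will vanish or reverse in this trial, because they give no AE rate, stopping rate or timing of either. The eradication comparison and the between-arm comparisons of AE rate and compliance rate are untouched. The change is worth making because it is cheap and corrects a causal claim that the planned test cannot carry.

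**What to change.** In Final SAP 6.3 and Table 5:

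- Retitle the analysis as an association between AEs and compliance, and present the adherence split by AE status as descriptive, without a p value.
- Count an AE as exposure only if its recorded onset precedes the stop or shortfall in intake, and state which AE window applies.
- Where the diary gives a stop day, report by arm the number of stops per person-day before and after first AE onset, and their ratio with a confidence interval. No Cox model is required.
- Keep the row on drugs discontinued because of AEs.

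The cost is a few lines of SAP text and some programming. AE onset is already recorded. The documents name no stop-date or daily dose field, so the sponsor must confirm that the diary yields a stop day. If it does not, the retitling and removal of the p value can still be done. With so few stoppers the rate ratio will be imprecise, and in the empiric arm it may not be estimable.

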6.4 Effect of compliance on eradication rate

Comparisons of eradication rate of one therapy between good and poor compliance will be performed in the ITT analysis populations who had UBT results using the Pearson's χ^2 , corrected χ^2 or Fisher's exact test.

7. Table Design

Table 1. Baseline characteristics

Variables	Tailored therapy	Empiric therapy	p value
Age, years (range)			
Gender (male/female)			
Diagnosis (Dyspepsia/PUD)			
Antibiotic resistance pattern			
Clarithromycin, n (%)			
Metronidazole, n (%)			
Levofloxacin, n (%)			
All-susceptible, n (%)			
Triple-resistant, n (%)			
Poor adherence*			
Loss of follow-up			

Final SAP

NUD, non-ulcer dyspepsia; PUD, healed peptic ulcer disease.

* Poor adherence, took less than 80% of drugs

Table 2. Eradication rate of each group in ITT and PP analysis

Analysis	Tailored therapy	Empiric therapy	Difference	p value for inequality*	p value for superiority **
ITT (% , n/N)					
95% CI					
PP (% , n/N)					
95% CI					

CI= confidence interval; ITT = intention-to-treat; PP = per-protocol.

* The *p* values were for testing the difference between tailored therapy group and empiric therapy group.

** The *p* values were for testing the superiority of tailored therapy group to empiric therapy group.

Table 3. antibiotic resistance pattern of ITT population

antibiotic resistance pattern (CLA-MET-LEV)	ITT population	Tailored therapy	Empiric therapy
All susceptible			
S-S-S			
Single resistant			
R-S-S			
S-R-S			
S-S-R			
Dual resistant			
R-R-S			
R-S-R			
S-R-R			
Triple resistant			
R-R-R			

CLA, clarithromycin; LEV, levofloxacin; MET, metronidazole; R, resistant; S, susceptible.

Table 4. Eradication rates of tailored and empiric therapy in the presence of antibiotic resistance in the per-protocol population

PP population	Tailored therapy	Empiric therapy	p value
Clarithromycin resistance			
Susceptible			
Resistant			
Metronidazole resistance			
Susceptible			
Resistant			
Levofloxacin resistance			
Susceptible			
Resistant			
Resistance pattern (Clarithromycin-Metronidazole-Levofloxacin)			
S-X-X			
R-S-X			
R-R-S			
R-R-R			

R=resistant; S=susceptible; X=resistant or susceptible.

Table 5. Adverse events and adherence in the treatment groups

Variables	Tailored therapy	Empiric therapy	p value*
Total, n/N (%)			
AE grade			
None/Mild/Moderate/Severe			
AE variety			
Taste alteration			
Dyspepsia			
.....			
.....			
.....			

Skin rash

Discontinued drugs

because of AEs

Good Adherence (Took at least 80% of drugs)

Subjects without AEs

Subjects with AEs

Total

AE, adverse event.

Summary of Statistical Analysis Plan Changes

Change	Original	Final
1. Sample size estimation	Assuming 95.7% eradication rate of tailored therapy in our trial, 88.8% eradication rate of empirical therapy, a superiority margin of >0 , a power of 80%, an alpha of 0.05 (one-sided), a ratio of 3:1, at least 340 subjects in susceptibility-based therapy and 114 subjects in empirical therapy will be required to show superiority of susceptibility-based therapy over empirical therapy on the basis of H. pylori eradication rate. Taking into consideration of 10% lost to follow-up, at least 500 participants (374 for tailored therapy and 126 for empiric therapy) is expected to be recruited for the study.	Assuming 96.5% eradication rate of tailored therapy in our trial, 88.9% eradication rate of empirical therapy, a superiority margin of >0 , a power of 80%, an alpha of 0.05 (one-sided), a ratio of 3:1, at least 260 subjects in susceptibility-based therapy and 87 subjects in empirical therapy will be required to show superiority of susceptibility-based therapy over empirical therapy on the basis of H. pylori eradication rate. Taking into consideration of 10% lost to follow-up, at least 382 participants (286 for tailored therapy and 96 for empiric therapy) is expected to be recruited for the study
3.1 presentation of	Variables of baseline characteristics collected are age (years), gender (male/female), diagnosis (Dyspepsia/PUD), clarithromycin-taking	Variables of baseline characteristics collected are age (years), gender (male/female), diagnosis (Dyspepsia/PUD), clarithromycin-taking

Summary of SAP changes

baseline characteristics
	
history, 23S rRNA mutation, antibiotic resistance pattern, poor adherence, and loss of follow-up. The following table shows the types and presentation of variables.
	
history, 23S rRNA mutation, antibiotic resistance pattern, poor adherence, and loss of follow-up. The following table shows the types and presentation of variables.


6. Additional analyses
	
6.3 Effect of 23S rRNA mutation on eradication rate
 
Comparisons of eradication rate of clarithromycin-containing therapy between strains with 23S rRNA mutation and those without 23S rRNA mutation will be performed in the PP analysis populations using the Pearson's χ^2, corrected χ^2 or Fisher's exact test.
 
6.4 Sensitivity, specificity, positive predictive value and negative predictive value of molecular genetic assays in clarithromycin resistance identification
 
Using culture based antibiotic susceptibility testing as the gold standard, sensitivity, specificity, positive predictive value (PPV) and negative predictive value (NPV) of 23S rRNA mutation in identification of H. pylori resistance to clarithromycin will be
	
6.3 Effect of 23S rRNA mutation on eradication rate (Deleted)
 
Comparisons of eradication rate of clarithromycin-containing therapy between strains with 23S rRNA mutation and those without 23S rRNA mutation will be performed in the PP analysis populations using the Pearson's χ^2, corrected χ^2 or Fisher's exact test.
 
6.4 Sensitivity, specificity, positive predictive value and negative predictive value of molecular genetic assays in clarithromycin resistance identification (Deleted)
 
Using culture based antibiotic susceptibility testing as the gold standard, sensitivity, specificity, positive predictive value (PPV) and negative predictive value (NPV) of 23S rRNA mutation in identification of H. pylori

Summary of SAP changes

	estimated.	resistance to clarithromycin will be estimated.
7. Table Design	
Table 1. Baseline characteristics
 
Table 4. Eradication rates of tailored and empiric therapy in the presence of antibiotic resistance in the per-protocol population
	
In Table 1, clarithromycin-taking history and 23S rRNA mutation were deleted.
 
In Table 4, subgrouping according to 23S rRNA mutation was deleted, and subgrouping according to levofloxacin resistance and antibiotic resistance pattern (Clarithromycin-Metronidazole-Levofloxacin) was added.

